4.8.1. Qualitative interviews

At the enrollment visit, a subset of 15-18 HIV negative eligible women and 20-25 eligible couples will be purposively selected and invited for in-depth qualitative interviews (Eligibility is defined as those who meet the criteria for enrollment as described in section 3.3 of the protocol). Half of the sample of in-depth respondents will be obtained from those who refuse to enroll in the study, to assess their concerns about study participation and their understanding and opinions about research and clinical trials.

4.8.2. Focus groups

4-6 focus group discussions will be conducted, each with 6-8 participants. These will be selected purposively from those women and couples who are eligible to participate in the cohort and who are willing to participate in the focus group. They will be selected at the enrollment visit. In-depth interviews and focus group discussions will be conducted by a pair of trained interviewers and facilitators. They will be conducted in Hindi / Marathi (local languages).

4.8.3. Qualitative Data Collection and Analyses

Where focus group discussion participants and in-depth interview participants are willing, tape recorders will be used. Field notes will be expanded and tapes will be transcribed and translated into English. Data will be analyzed using Nudist or AtlasTi software for ethnographic data according to the following themes:

- Participant / Respondent Understanding of the term "research"
- Understanding the term "informed consent"
- Understanding of the term "randomization"
- Understanding of the term "placebo"
- What are the barriers to participation
- Categories of the different types of barriers to participation (e.g personal family, husband or partner refuses permission, work, stigma)
- Attitudes / beliefs towards participation in research trials

These themes will be further compared across gender, those who are willing to participate versus those who are not, levels of education and age. The analysis of the qualitative data will focus on those barriers to participation and retention that can be addressed at the clinic level and through modification in the study or project protocols (e.g. using pictorial charts to explain clinic procedures simply and clearly) and those that cannot be addressed at the clinic level (e.g. inability to participate because loss of wages/work). Input from the community advisory board will be sought to develop ways to reduce possible costs (e.g. child care, transportation, food) to those enrolled in the study. For HIV negative women participants, efforts will be made to understand and address whether their participation in the study will have negative consequences (i.e. violence, stigma) in their relationships with spouses and families.

4.9 Transition from Preparedness Studies to HPTN Clinical Trial Implementation

While these preparation studies are underway, we will also be participating in the final development and planning for the HPTN 035 and 052 trials planned for the site in Pune. Therefore, we require a plan for transitioning from preparedness work to protocol implementation. We propose that the HPTN 034 protocol team undertake an interim analysis of the primary endpoints of this protocol, when the final protocols for the Phase III microbicide trial and the ART trial are submitted to the PSRC for review. Based upon the results of these analyses

and the time-lines for implementation of the clinical trials, the protocol team in consultation with the EC and PRC will determine whether the activities focused upon addressing any of the primary endpoints will be terminated and resources shifted towards plans for trial implementation.

There are 2 Phase III trials (035 and 052) and 1 Phase I/II trial (047) planned for this site in Pune. We have conducted multiple large simultaneous cohort studies and phase I clinical trials in the past. However, we must plan the conduct of this preparation study and the initiation of these clinical trials carefully to ensure the successful implementation and coordination of these activities and our resources. It is our expectation that the timing of the initiation of the subsequent HPTN clinical trials in Pune will be carefully coordinated. For both of the proposed phase III trials, the Pune site is proposed as one site in a multi-centered trial. Given the time and effort required to finalize and review each of these protocols within the HPTN, NIAID, IRBs and host countries, we do not anticipate that the trials will be initiated simultaneously. However, with planned and coordinated initiation of these trials, we do have the capacity for simultaneous enrollment and follow-up for multiple HPTN clinical trials. In addition, we have selected the trials for participation carefully. Each trial, as currently planned, will recruit distinct subjects from our clinics. Our current estimated timeline for the activities in Pune, based on the status of each of the trial protocols is as follows:

Pune Projected HPTN Protocol Initiation Timeline

Sept	March	Sept	March	Sept	March
2000	2001	2001	2002	2002	2003
I	I	I	I	I	I
		^	^	٨	
	1	HPTN 034	Interim	HPTN 052	
			Analysis*		
		۸	Λ		
		HPTN 047	HPTN 035		

*Interim HPTN 034 Analysis

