Division of AIDS (DAIDS) US National Institute of Allergy and Infectious Diseases (NIAID) US National Institutes of Health (NIH)

I, the Principal Investigator, agree to conduct this study in full accordance with the provisions of this protocol. I agree to maintain all study documentation for a minimum of five years from the end of the study, unless directed otherwise by the HPTN CORE. Publication of the results of this study will be governed by HPTN and DAIDS policies. Any presentation, abstract, or manuscript will be made available by the investigators to the HPTN Manuscript Review Committee and DAIDS for review prior to submission.

I have read and understand the information in this protocol and will ensure that all associates, colleagues, and employees assisting in the conduct of the study are informed about the obligations incurred by their contribution to the study.

Name of Principal Investigator

Signature of Principal Investigator

Date

HPTN Protocol 034 HPTN HIV Incidence and Participant Retention Protocol, Pune, India PROTOCOL SUMMARY

Design: This protocol is a cohort study of HIV incidence in patients attending STD clinics in Pune, who will be eligible for screening and participation in 2 upcoming HPTN clinical trials of vaginal microbicides (HPTN 035) and antiretroviral drugs (HPTN 052).

Population:	400 adult HIV-uninfected non-sex, worker women attending STD clinics and 400 HIV discordant sexual couples from Pune, India.
Study Duration:	Accrual will require 12 months and participants will complete one year of follow-up. Therefore, the entire study should be completed within approximately 24 months.

Primary Objectives:

- 1. To determine the current incidence of HIV among a cohort of 400 newly identified high-risk, women in Pune, as well as among 400 HIV-uninfected partners of HIV-infected persons.
- 2. To determine the retention rate in high-risk women, as well as HIV discordant couples, among a target population eligible for screening for upcoming HPTN 035 and 052 trials.

Primary Endpoints:

- Current HIV seroconversion rates in HIV-uninfected participants.
- Retention rates in high-risk women, as well as discordant couples.

Secondary Objectives:

- 1. To assess risk factors for HIV and other STDs.
- 2. To identify and address potential barriers to participation and high-level retention (>95% 1 year retention) for the upcoming HPTN clinical trials.

Secondary Endpoints:

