Previous prevention trial planning efforts have indicated that Phase III studies of HIV prevention interventions will require the participation of large numbers — from several hundred to several thousand — of persons at high risk for HIV infection. In addition to accruing large numbers of participants, research centers conducting Phase III HIV prevention studies must retain participants in extended periods of follow-up — from several months to several years — in order to preserve the statistical power of the study as well as avoid potentially biased results that may not accurately reflect the impact of the intervention in the target population. Some have recently argued that a greater than 95%

1 year retention is required for any HPTN Phase III clinical trial. Our HPTU in Pune is committed to achieving the enrollment and retention required for such a trial.

The design of Phase III HIV prevention trials to be conducted in the HPTN will depend on the efficacy or effectiveness of intervention being studied as well as the interplay of the four parameters referenced above: the number of participants enrolled, the HIV incidence rate among enrollees, the duration of follow-up, and the number of participants retained in follow-up.

Our site in Pune has already conducted two Phase I microbicide trials, and is well prepared for initiating the upcoming PRO 2000/5 Gel (P) Phase I trial (HPTN 047). We are currently preparing the protocol, in anticipation of initiating this trial within the next 4-6 months. In anticipation of the initiation of the HPTN 035 trial within the next year and the HPTN 052 trial within the next 24 months (see time-line chart in Section 4.9 below), we have identified a number of specific research objectives that we believe are necessary to ensure the successful and efficient initiation of these HPTN trials. This study will also provide new data important for the design of future HIV prevention trials.

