Our previous experience with enrollment and follow-up for clinical trials suggests that this 81% retention rate will be increased and sustained with effective community education about the specific risks, benefits and objectives of participating in HPTN clinical trials. However, this HPTN protocol will target a goal of at least 90-95% 1 year retention in our observational cohort for newly identified and enrolled high-risk individuals, in anticipation of the need for this level of retention for the upcoming HPTN trials. With a current follow-up rate of >80% for our observational study of HIV transmission and follow-up rates of >90% for our other prospective clinical studies, including three HIV clinical trials, we are confident that this protocol will help us identify the procedures required to achieve the excellent retention of participants required for the HPTN 035 and 052 trials.

One of the proposed HPTN trials for Pune (HPTN 052) will enroll HIV discordant couples. The Pune site has some experience through the HIVNET 023 couples study with screening, enrollment and follow up of discordant couples. However, this 034 protocol specifically includes efforts to identify and enroll up to 400 HIV discordant couples in an observational cohort study. This will provide essential experience and a preliminary base for the enrollment of discordant couples into future HPTN clinical trials. NARI has a HIV Reference Clinic facility on the premises of National Institute of Virology, Pune. This site is proposed for recruiting HIV discordant couples in various clinical trials. In addition, we have also successfully negotiated a clinic space in Talera Hospital in Chinchwad, an adjoining Municipal hospital and we have initiated an HIV reference clinic in this center that will also serve as a referral source for HIV discordant couples. In addition, through community outreach to local physicians, hospitals and clinics, NARI has become a regional reference center for the care of HIV infected individuals. We anticipate that this referral base will also provide additional opportunities to identify HIV-infected index partners for enrollment of discordant couples.

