4 STUDY PROCEDURES

The objective of our efforts will be to ensure the availability of a sufficiently large cohort of high-risk men and women for participation in the multiple HPTN clinical trials, with incident HIV infection as the primary outcome measure. Our goal will be to continue to screen 2000 new male and female high-risk patients/year, with an expected HIV prevalence of 20%. Of the 1600 HIV-uninfected individuals, we will anticipate enrollment of approximately 400 new non-sex worker women over the first 12 months into this follow-up study of HIV seroconversion. We will also enroll 400 HIV-discordant couples. The estimated study time line is outlined in the chart below.

		HPTN 034 Initiation ▼				
Sept	March	Sept	March	Sept	March	Sept
2000	2001	2001	2002	2002	2003	2003
I	I	I	I	I	I	I

HPTN 034 Timeline

HPTN 034 Screening/Enrollment (n=1200 enrolled, 400 HIV- women +400 HIV discordant couples) I------I HPTN 034 Follow-up

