5.4 Data Monitoring and Analysis

Close cooperation between the study site Investigator, Protocol Coordinator, Biostatistician, Data Managers, and other study team members will be necessary in order to track study progress, respond to queries about proper study implementation, and address other issues in a timely manner. Rates of accrual, follow-up, and protocol compliance will be monitored closely by the study team. Representatives of the HPTN CORE and SDMC also will evaluate these rates on a regular basis. If unexpected concerns arise, they will be addressed according to HPTN standard operating procedures.

The two primary objectives of this protocol will be:

- To determine the current incidence of HIV among a cohort of 400 newly identified high-risk, HIV-negative women in Pune. In addition, a separate estimate of the HIV incidence among 400 HIV-uninfected partners of HIV-infected subjects will also be estimated separately.
- To determine the retention rate in high-risk women, as well as HIV discordant couples.

Corresponding to each of the primary study objectives and outcomes, the following primary data analyses will be performed:

- An HIV seroincidence (and 95% confidence intervals) for the cohort study will be computed as the total number of HIV seroconversions divided by the total number of person-years of follow-up. Separate estimates of seroincidence will be calculated for the 400 women and the 400 HIV-uninfected partners.
- The number of enrolled participants retained for each study follow-up interval will be tabulated. Retention rates also will be calculated. The denominator for these calculations will be the total number of participants enrolled in the study. The numerator will include all participants who complete a Follow-up Pre-Test Visit during the interval and/or are known to have become HIV-infected or to have died during a previous interval. Overall retention rates will be calculated for all 1200 subjects. In addition, the retention rates of the subset of 400 women and 400 discordant couples will be separately calculated.
- Univariate and multivariate analysis will be performed for risk factors for incident HIV infection.

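### Section 5.4 has no exit category for a participant who leaves 034 to join HPTN 035 or 052, so a transfer would be scored as a failure of retention

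*Supplement*

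**What the plan says.** **The pool.** The Protocol Summary describes 034 participants as people "who will be eligible for screening and participation in 2 upcoming HPTN clinical trials". Section 4 gives the aim as to "ensure the availability of a sufficiently large cohort of high-risk men and women for participation in the multiple HPTN clinical trials". Section 1.3.6 calls the couples cohort "a preliminary base for the enrollment of discordant couples into future HPTN clinical trials". Section 4.9 adds "Each trial, as currently planned, will recruit distinct subjects from our clinics"; in context this separates the trials from one another and does not exclude 034 members.

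**Timing.** Section 1.1 expects both 034 primary objectives to be met before the trials begin. Yet it also writes "In anticipation of the initiation of the HPTN 035 trial within the next year and the HPTN 052 trial within the next 24 months", and the Version 1.0 Protocol Summary says "the entire study should be completed within approximately 24 months". The chart in 4.9 marks 034 at September 2001, 035 at March 2002 and 052 at September 2002.

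**Transition rule.** After "we require a plan for transitioning from preparedness work to protocol implementation", section 4.9 sets out an interim analysis of the primary endpoints when the trial protocols go for review. A decision follows on whether 034 activities stop. Section 1.1 has a matching continue-or-terminate rule.

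**Analysis.** In 5.4 the retention denominator is everyone enrolled. For the numerator: "The numerator will include all participants who complete a Follow-up Pre-Test Visit during the interval and/or are known to have become HIV-infected". Deaths are credited too, and both kinds of event must fall in an earlier interval. Incidence is seroconversions over total person-years. Section 3.5 allows withdrawal for any reason and does not mention entry into another trial. Under the revised Clarification Memo #1, a visit more than 22 days off schedule is missed.

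**Amendment.** The 2004 Letter raises the cohorts to 540 women and 530 couples and lengthens accrual and follow-up. It adds no rule for people who move and does not redraw the chart.

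**The concern.** Retention is one of the two primary endpoints, and its purpose is to show whether the site can hold participants at the level 035 and 052 will need. Section 5.4 already accepts that two kinds of exit, infection and death, are not failures of retention. It omits the exit that the study exists to prepare for.

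A woman who joins 035, or a couple who join 052, and who stop attending 034 would be indistinguishable in the reported rate from people who disappeared. The site aims for 90-95% at one year (section 1.3.6), or above 95% (section 2.2). A modest number of transfers could move the estimate from one side of those marks to the other and make a well-functioning site look as though it loses participants.

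**Working it through.** **1. The plan's own precision.** Half-width = 1.96 × √[p(1 − p)/n]. With p = 0.95 and n = 400 (section 5.3.2) this is 2.14 points, as stated. The Letter carries 2.14 over to n = 540, where the same formula gives 1.84.

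**2. Effect of transfers under 5.4 as written.** Let f be the share who leave for a trial before the visit in question. The documents do not give f, so a range is assumed. If moving is unrelated to whether the person would otherwise have been retained, reported retention = 0.95 × (1 − f):

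- f = 2%: 0.95 × 0.98 = 93.1%
- f = 5%: 0.95 × 0.95 = 90.3%
- f = 10%: 0.95 × 0.90 = 85.5%

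The share that shifts the estimate by a full half-width is 2.14/95 = 2.3%, or about 9 of 400. At n = 540 with the recalculated 1.84 it is 1.9%, or about 10 people.

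**3. After the fix.** With transfers out of the later denominator, the estimate stays at 95%. At n = 400 the half-width becomes 2.19 (5% moving, 380 left) or 2.25 (10%, 360 left). At n = 540 it becomes 1.89 or 1.94.

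**4. If movers are the better attenders.** Suppose every mover would have been retained. Censoring then gives (0.95 − f)/(1 − f): 0.93/0.98 = 94.9% at 2% and 0.85/0.90 = 94.4% at 10%. Counting transfers as retained returns 95%. Under independence the latter gives 0.95 × (1 − f) + f, which is 95.1% and 95.5%. The two analyses together stay within about 0.6 points of the truth in both cases.

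**5. Overlap on the 4.9 chart.** With uniform 12-month accrual and 12 months of follow-up:

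- Mean follow-up before month 6 (035 opens) is (1/12) × ∫₀⁶(6 − t)dt = 1.5 of 12 months, so 87.5% of person-time comes later.
- Mean follow-up before month 12 (052 opens) is 6 of 12 months, so 50% comes later.

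This shows that the chart and the expectation in 1.1 disagree. It does not forecast actual exposure. 034 began on 16 September 2002 (Clarification Memo #2), and the calculation supposes that 034 always continues. On the amended 17.5 + 17.5 months, a trial opening 12, 18, 24 or 30 months into 034 (assumed) would leave 76%, 47%, 20% or 4% of person-time after it.

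**6. Incidence.** People who leave add no further 034 person-time. Dilution arises only if they attend both studies. If 10% of the women's person-time were under an intervention with a 30-50% effect (both assumed), 5.6/100PY becomes 5.6 × (1 − 0.10 × 0.30) = 5.43 to 5.6 × (1 − 0.10 × 0.50) = 5.32. The stated interval is 3.37-8.74; an exact Poisson interval on 348 person-years gives 3.40-8.70. Censoring that 10% instead leaves 313 person-years and an interval of 3.29-8.90.

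**The case against.** **There is a transition plan.** Section 4.9 does not stop at saying that one is needed. It provides an interim analysis and a decision to continue or stop, and section 1.1 expects the objectives to be met first. This is right, and a reader who took the protocol to have no plan would be wrong. But the plan governs the study and its resources. Under continuation a mover is scored as lost. Under termination the denominator is still everyone enrolled. Neither branch classifies a person.

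**Transfers are inferred.** No section says that enrolled participants will be moved, and section 1.2.1 describes the women as representative of possible 035 participants. The 035 and 052 protocols, a natural home for co-enrolment rules, are not shown. This stands: the bias is conditional on transfers occurring.

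**The overlap may be small.** A reader might infer from the chart that most 034 person-time certainly falls after the trials open. The documents do not support that. The chart predates the actual start by a year, the Letter moves the planning horizon in 1.1 from two to three years, and the women's 470 person-years are counted to August 2004. If a trial opened at month 26 (assumed; November 2004), that date would already have passed. Only entrants after month 14 would still owe a month-12 visit: 3.5/17.5 = 20%, or 9/23 = 39% if accrual ran 23 months. A 10% transfer share before month 12 would then need about half or a quarter of them to move. The upper end of the assumed range is demanding on a late opening; the lower end is not.

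**Incidence.** A reader might also infer that the incidence estimate is materially diluted. No section plans attendance at both studies, 052 is randomised so not all co-enrolled time would be treated, and the shift is well inside the stated interval.

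**Conclusion.** The retention point holds in conditional form. As written, 5.4 scores a participant who leaves 034 for an HPTN intervention trial as not retained, and the study-level rule does not alter this. If 2-10% moved (assumed), a true 95% would be reported as about 93-86%; about 9 of 400 movers would use up the whole stated margin. These figures assume that moving is independent of being otherwise retained and that movers stop 034 visits. The documents fix neither the number of movers nor the trials' opening dates under the amended calendar, so the size cannot be settled. The incidence consequence is minor. Separately, section 1.1 and the 4.9 chart give different pictures of whether the trials open during 034, and they must be reconciled.

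**What to change.** Add to 5.4, with a cross-reference in 4.9: a participant who enters an HPTN intervention trial is administratively censored in 034 on that date (both members, for a couple). That participant leaves the retention denominator for later intervals and contributes person-years and seroconversions only up to that date. Show the number transferred beside each retention rate, and report a sensitivity analysis counting transfers as retained, since they may be the better attenders. Reconcile the timing statement in 1.1 with the 4.9 chart and redate the chart.

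The cost is a few sentences, one date per participant, some person-years given up, and a slightly wider retention interval (about 2.2-2.3 points at 5-10% transfer with n = 400). The change concerns scoring only. It does not set whether anyone may co-enrol.
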